8.5.2 Missing Endpoint Data

Missing endpoint data will not be imputed, and only observed data will be summarized.

8.6 Interim Analysis

An interim analysis of the safety and open-label efficacy data was conducted to assess the adequacy of the dose conversion strategy and the activity of SD-809 in treating chorea. Details can be found in Appendix 1.

8.7 Comments on Statistical Analysis

The following general comments apply to all statistical analyses and data presentations:

- Unless otherwise specified, all data will be summarized separately for the Rollover Cohort and the Switch Cohort.
- Summaries will include frequencies and percentages for categorical data and the number of observations, mean, standard deviation, median, minimum, and maximum for continuous data.
- Duration variables will be calculated using the general formula: (end date – start date) + 1.
- Unless specified otherwise, for subjects in the Switch cohort, the baseline value is the last available value prior to the first administration of SD-809 on Day 1. For Rollover subjects from the First-HD study, for assessments that were scheduled to be performed at Week 13 of that study or the Baseline visit of the ARC-HD study, the baseline value is the last available off-treatment (at least 4 days after the last administration of study drug) value prior to administration of SD-809 on Day 1. For assessments that were not scheduled to be performed at Week 13 of the First-HD study or at the Baseline visit of the ARC-HD study, the baseline value is the last available value prior to administration of study drug on Day 1 of the First-HD study. For the Switch cohort, the baseline value used for calculating change from baseline for TMC and the total motor score will be the mean of the values from the Screening and Baseline visits.
- If the reported value of a clinical laboratory parameter cannot be used in a statistical summary table (e.g., a character string is reported for a parameter of the numeric type), a coded value must be appropriately determined and used in the statistical analyses. In general, a value or lower or upper limit of normal range such as '<10' or '<5' will be treated as '10' or '5', respectively, and a value such as '>100' will be treated as '100.' However, the actual values as reported in the database will be presented in data listings.
- Individual subject listings of all data represented on the eCRFs will be provided to facilitate the investigation of tabulated values and to allow for the clinical review of all data.
- Version 9.4 of SAS statistical software package will be used to provide all summaries, listings, and graphs described in this document.

- All raw data will be presented to the original number of decimal places. Means and medians will be presented to one more decimal place than the raw data. Standard deviations will be presented to two more decimal places than the raw data.
- The denominator for percentages will be based on the number of subjects or observations with non-missing data appropriate for summary purposes. Unless otherwise noted, all percentages will be presented to one decimal place.

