STATISTICS	
Safety:
 
Safety data will be summarized descriptively for the overall population and based on prior treatment [SD-809 ER or placebo (Rollover subjects) or tetrabenazine (Switch subjects)]. Descriptive statistics will be calculated for quantitative data and frequency counts and percentages will be provided for categorical data. The nature, frequency, and severity of adverse events will be tabulated for all subjects combined and by prior treatment. Baseline, within study, end of study, and change-from-baseline values for clinical laboratory evaluations and vital signs will be summarized as appropriate.
 
Treatment-emergent adverse events and laboratory, vital sign, and ECG parameters will be summarized. In addition, change from baseline will be summarized for laboratory and vital sign parameters. Shift tables will be provided for clinical laboratory results. ECG results will be classified as normal and abnormal and summarized.
 
Descriptive statistics of change-from-baseline for Rollover subjects will utilize the Baseline from Study SD-809-C-15 (C-15 Baseline) and the Baseline from the present study (C-16 Baseline), as appropriate, and will be specified in the Statistical Analysis Plan.
 
Pharmacokinetics:
 
A population pharmacokinetic analysis will be performed using data from all subjects switching from TBZ to SD-809 ER in this study together with data obtained from subjects in Study SD-809-C-15 to examine the pharmacokinetics of SD-809 and TBZ and to explore the potential effect of various covariates on the pharmacokinetics of SD-809 and TBZ. The population pharmacokinetic analysis will be discussed in detail in a prospective Statistical Analysis Plan.

SCHEDULE OF EVENTS A – SUBJECTS SWITCHING FROM TETRABENAZINE

Study Week →	Screening			Long Term Treatment										Follow up		Unscheduled		
	Up to -4	-1	Baseline	Dose Adjustment				7	8	15	28	28 + q13 wks	End of Treatment	1 wk FU	4 wk FU			
Visit Window (days) →		± 3	0	± 1													n/a	
Visit →	Screening	T1	V1	V2	T2	T3	V3	T4	V4	V5	V6	Vx ¹⁷	End Tx/ET	FU	FFU	UV ¹⁸	UT C	
Activity Visit type →	V	TC	V	V	TC	TC	V	TC	V	V	V	V	V	V	TC	V	TC	
Evaluate/Adjust Dose				X	X	X	X									X	X ³	
Evaluate Capacity for consent	X																	
Informed Consent/Assent	X																	
Assign Subject ID	X																	
Assign Unique ID	X																	
Research Advance Directive**	X																	
Selection Criteria	X		X															

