8.3 Safety Analyses

Safety and tolerability will be assessed throughout the study by monitoring the following parameters:

 • Adverse events (AEs) • Clinical laboratory tests • Physical examination • Vital signs • 12- lead ECGs • Epworth Sleepiness Scale (ESS) 	
 • Columbia Suicide Severity Rating Scale (C-SSRS) • Unified Huntington’s Disease Rating Scale (UHDRS) • Swallowing Disturbance Questionnaire (SDQ) • Unified Parkinson’s Disease Rating Scale (UPDRS), dysarthria item • Barnes Akathisia Rating Scale (BARS) • Hospital Anxiety and Depression Scale (HADS) • Montreal Cognitive Assessment (MoCA©)
---	--

Safety data will be summarized descriptively for the overall population and based on prior treatment [SD-809 ER or placebo (Rollover subjects) or tetrabenazine (Switch subjects)]. Descriptive statistics will be calculated for quantitative data and frequency counts and percentages will be provided for categorical data. Descriptive statistics of change-from-baseline for Rollover subjects will utilize the Baseline from Study SD-809-C-15 (C-15 Baseline) and the Baseline from the present study (C-16 Baseline), as appropriate, and will be specified in the Statistical Analysis Plan.

The nature, frequency, and severity of adverse events will be tabulated for all subjects combined and by treatment. Baseline, within study, end of study, and change-from-baseline values for clinical laboratory evaluations and vital signs will be summarized as appropriate.

Treatment-emergent adverse events and laboratory, vital sign, and ECG parameters will be summarized. In addition, change from baseline will be summarized for laboratory and vital sign parameters. Shift tables will be provided for clinical laboratory results. ECG results will be classified as normal and abnormal and summarized.

8.4 *Safety Endpoints*

The following safety endpoints will be assessed:

- Incidence of adverse events (AEs), serious AEs, severe AEs, drug related AEs, AEs leading to withdrawal during the following periods:
 - Overall
 - During titration in Rollover subjects (up to 8 weeks)
 - During dose adjustment in Switch subjects (up to 4 weeks)
 - During long term treatment
- Observed values and changes from baseline in clinical laboratory parameters (hematology, chemistry, and urinalysis)
- Observed values and changes from baseline in vital signs
- Observed values in ECG parameters and abnormal findings

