- ** Data (Week 13) from Study SD-809-C-15 will be utilized as part of Baseline assessment. Additional specific activities required at this visit are denoted by an “X”
- 1 Assessment transferred from Screening or Baseline evaluation in Study SD-809-C-15
 - 2 Perform orthostatic blood pressure and pulse after subject is in standing position for at least 3 minutes.
 - 3 Assessments to be completed at Investigator’s discretion
 - 4 Brief physical examination, which includes evaluation of the cardiovascular, respiratory, and abdominal systems.
 - 5 The C-SSRS Since Last Visit version is administered at all visits for Rollover subjects
 - 6 Study medication supply will be ordered (See Operations Manual for further details).
 - 7 Subjects who withdraw early from the study should have a single blood sample collected for PK at the Early Termination Visit if the last dose was within the prior 48 hours, if possible. Subjects who experience an SAE should have a single blood sample collected for metabolites of SD-809 within 48 hours of SAE, if possible.
 - 8 For subjects on allowed doses of citalopram or escitalopram:
 - Week 2: A 12-lead ECG is required at this visit.
 - Week 4: If the dose of study drug has been increased since the last ECG, a 12-lead ECG is required at this visit.
 - 9 After Week 28, perform clinic visits every 13 weeks until the End of Treatment Visit. Obtain safety labs and urine pregnancy test every 26 weeks after Week 28, and perform UHDRS-TFC every 52 weeks after Week 28.
 - 10 For subjects requiring an Unscheduled Clinic Visit for any reason, assessments denoted with X should be performed; all other assessments are as indicated at Investigator’s discretion (see Section 6.5 of the protocol).

5 Data Management

Complete details of data management will be described in a separate Data Management Plan.

6 Definition of Population

Safety Population: The Safety Population will include all subjects who were administered any study drug. Subjects who are assigned a subject number but withdrew prior to dosing will not be included in the Safety Population. If relevant, details of their participation and reason for withdrawal will be listed separately in the CSR.

Unless specified otherwise, all data will be summarized for the Safety Population. In addition, two subsets of the Safety Population are defined:

- Rollover Cohort: Successfully completed SD-809-C-15 (First-HD) prior to enrollment into SD-809-C-16 (ARC-HD)

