9.9 Safety Analyses

Safety will be assessed using the Safety Population.

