9.9.1 Adverse Events

Adverse events will be coded using version 16.1 of the Medical Dictionary for Regulatory Activities (MedDRA); the MedDRA version will be noted in the CSR. Treatment-emergent AEs (TEAEs) are events that 1) begin after treatment with study drug in the current study and that are not present at baseline or 2) if present at baseline, have worsened in severity. For AEs with missing start dates, the AE will be considered treatment-emergent unless there is additional information indicating that the AE started prior to the first treatment. All analyses of TEAEs will be performed separately for TEAEs that occurred during the titration period (for Rollover subjects only), during the dose-adjustment period (for Switch subjects only), during the extended dose-adjustment period (for Switch subjects only), during the stable dose period, and during the entire treatment period. To be conservative, all adverse events that occurred during the follow-up period will be counted as events that occurred during the last available treatment period. In order to be included in the analysis for a given time period, a subjects must have at least one visit during the time period.

For the Switch cohort, an overview of AEs occurring during the Screening period will present the number and percentage of subjects in the following categories:

- Any AEs
- Any serious AEs (SAEs)
- Any severe AEs
- Any AE(s) leading to death

An overview of TEAEs will present the number and percentage of subjects in the following categories:

- Any TEAEs
- Any serious TEAEs

-
- Any severe TEAEs
 - Any treatment-related TEAEs
 - Any TEAEs resulting in dose reduction
 - Any TEAEs resulting in dose suspension
 - Any TEAEs resulting in withdrawal from the study
 - Any treatment-related TEAEs resulting in withdrawal from the study
 - Any TEAEs resulting in dose reduction, dose suspension, or withdrawal from the study
 - Any TEAE(s) leading to death

TEAEs, serious TEAEs, TEAEs that led to dose reduction, TEAEs that led to dose suspension, TEAEs that led to withdrawal from the study, TEAEs that occurred in at least 4% of Rollover or Switch cohort subjects in the Safety Population across all time periods, will be summarized at the subject level by MedDRA system organ class (SOC) and preferred term using frequencies and percentages.

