Exposure adjusted incidence rates (number of patients with an event per person-year) will also be presented for the above TEAE overview categories, all preferred terms, and selected AEs of interest by patient cohort and study (First Active in C15, First Placebo in C15, Rollover in C16, and Switch in C16). AEs of agitation, somnolence, insomnia, anxiety and fall will be defined as events with matched preferred terms. In addition, AEs with selected preferred terms will be combined into the AEs of interest as follows:

- Akathisia and Restlessness: Akathisia, Hyperkinesia, Psychomotor hyperactivity, Restlessness, Agitation
- Dysphagia: Aphagia, Dysphagia
- Parkinsonism: Akinesia, Bradykinesia, Cogwheel rigidity, Freezing phenomenon, Hypertonia, Masked facies, Muscle rigidity, On and off phenomenon', Parkinsonian crisis, Parkinsonian gait, Parkinsonian rest tremor, Parkinsonism, Parkinson's disease, Resting tremor
- Suicidality: Completed suicide, Depression suicidal, Intentional overdose, Intentional self-injury, Poisoning deliberate, Self-injurious ideation, Suicidal behavior, Suicidal ideation, Suicide attempt.
- Depression: all preferred terms containing “depression”

Incidence rate will be calculated as:

Number of patients with given event/ Person-years for the event

Person-years for a selected event are defined as the sum of exposure days across all subjects divided by 365.25. Subjects with an event of the given type contribute days from the date of their first treatment dose until the date of the first event of the given type. Subjects without an event of the given type contribute days from date of their first treatment dose until their treatment end date. Events that occurred after the last dose date of each study period were not included.

TEAEs and treatment-related TEAEs, categorized by system organ class, preferred term, and maximum severity (mild, moderate, or severe), will be summarized by study period using counts and percentages. In addition, TEAEs, categorized by system organ class, preferred term, and relationship to study drug (unrelated, related), will be summarized by study period using counts and percentages. TEAEs that are classified as possibly, probably, or definitely related to study drug on the AE eCRF, or for which the relationship to study drug is missing, will be considered treatment related. Unrelated AEs include those classified as unrelated or unlikely related on the AE eCRF.

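### The SAP does not carry the protocol's prior SD-809 versus prior placebo split of Rollover subjects into its safety tables, and does not declare the change

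*SAP*

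**What the plan says.** **Protocol.** Section 8.3 says safety data will be "summarized descriptively for the overall population and based on prior treatment [SD-809 ER or placebo (Rollover subjects) or tetrabenazine (Switch subjects". The Statistics part of the synopsis says the same of adverse events: "The nature, frequency, and severity of adverse events will be tabulated for all subjects combined and by prior treatment".

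**SAP.** The general rule in 8.7 is "Unless otherwise specified, all data will be summarized separately for the Rollover Cohort and the Switch Cohort". Section 6 defines the Rollover Cohort as those who successfully completed C-15, whichever arm they were in. The safety section then specifies:

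- 9.9.1, periods: "All analyses of TEAEs will be performed separately for TEAEs that occurred during the titration period (for Rollover subjects only"), followed by the dose-adjustment, stable-dose and entire-treatment periods.
- 9.9.1, common events: the table covers "TEAEs that occurred in at least 4% of Rollover or Switch cohort subjects in the Safety Population across all time periods".
- 9.9.1, exposure-adjusted rates: presented "by patient cohort and study (First Active in C15, First Placebo in C15, Rollover in C16, and Switch in C16").
- 9.9.1, CYP2D6 repeats: split by CYP2D6 status only.
- 9.9.2 to 9.9.7: vital signs, ECGs, laboratory tests and rating scales, with no mention of prior arm.

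SAP 8.10 lists two changes from the protocol: the compliance range, and the move of total maximal chorea (TMC) and total motor score from safety to efficacy.

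**The concern.** Protocol 5.2.3 has every Rollover subject restart at the same dose whatever the C-15 arm. During titration, prior-placebo subjects therefore meet SD-809 for the first time, while prior-SD-809 subjects are being re-exposed.

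The two groups also reached the study by different routes. Protocol 3.1 admits only those who stayed in C-15 through Week 13 and had no ongoing serious or severe adverse event. Prior-SD-809 subjects met that condition after assignment to the drug, and prior-placebo subjects did not. This is a reason the titration rates might differ, not evidence that they do.

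The first study objective concerns the safety and tolerability of titration as well as maintenance. Without the split, a reader of the titration tables cannot see whether the Rollover figure describes both groups or averages over a difference. The protocol's grouping would have shown this, and a reader of the study report would not be told that it had been dropped.

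**Working it through.** **1. Mapping the protocol's groups onto the SAP**

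| Protocol 8.3 group | SAP 9.9 safety tables |
|---|---|
| Overall | Unclear: section 6 points to the whole Safety Population, 8.7 to separate cohorts |
| Prior tetrabenazine | Kept, as the Switch Cohort |
| Prior SD-809 ER | Merged into Rollover |
| Prior placebo | Merged into Rollover |

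The loss is the split inside Rollover. In the exposure-adjusted table, the two columns that look like a split by arm are C-15 data; C-16 has a single Rollover column.

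**2. Is the split available?** Yes. SAP 8.4 keeps C-15 assignments blinded only until that study is locked and unblinded. SAP 9.7 already uses prior-SD-809 and prior-placebo groups for TMC and total motor score. That use covers change from Week 8 only, so it starts where titration ends.

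**3. Is the change declared?** No. Neither change in 8.10 concerns the grouping of safety data.

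**4. Size (illustration).** The only figure in the plan to reproduce is planned enrolment: 36 Switch + 80 Rollover = 116, which agrees. The documents as available give neither the C-15 allocation nor event rates, so the following inputs are assumed.

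Let p be the first-exposure titration proportion, s the prior-SD-809 share of Rollover, and r the risk ratio of re-exposed to first-exposed.

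- Pooled proportion = (1 − s)p + s·r·p = p[1 − s(1 − r)].
- Relative gap, (first-exposure − pooled)/first-exposure = s(1 − r).

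With s = 0.5 and p = 20%:

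| r | Relative gap | Pooled | First-exposure minus pooled |
|---|---|---|---|
| 0.5 | +25% | 15.0% | +5.0 points |
| 0.75 | +12.5% | 17.5% | +2.5 points |
| 1 | 0 | 20.0% | 0 |
| 1.25 | −12.5% | 22.5% | −2.5 points |

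For s from 0.375 to 0.625 and r from 0.5 to 1.25, the extremes are 0.625 × 0.5 = +31% and 0.625 × (−0.25) = −16%. The range passes through zero. The formula applies to proportions, not to exposure-adjusted rates.

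**5. What the split could show.** Assume 40 subjects per prior arm.

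- Zero events: the exact 95% upper limit is 1 − 0.025^(1/40) = 8.8%, against 1 − 0.025^(1/80) = 4.5% for the Rollover total.
- 8/40 against 4/40: the exact intervals are 9.1–35.6% and 2.8–23.7%. The total, 12/80, has 8.0–24.7%.
- Difference: 0.10 ± 1.96·√(0.2·0.8/40 + 0.1·0.9/40) = 0.10 ± 0.155, that is −5.5 to +25.5 points.
- A two-sided 5% z-test at true rates of 20% and 10% would have about 24% power.

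**The case against.** The case against has several parts, and some of it stands.

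- **The protocol is not uniform.** The adverse event sentence in Protocol 8.3 says by treatment, without the word prior, and the opening of section 8 does the same and leaves details to the SAP. This is fair, but the general sentence in 8.3 names the three prior treatments, and leaving details to the SAP does not cover an undeclared change of grouping.
- **The endpoint is reported.** Protocol 8.4 defines titration incidence in Rollover subjects without a split, and the SAP delivers it. This stands.
- **The design treats Rollover as one titration cohort.** All have about a week off drug and restart alike. Protocol 3.2 lists the prior exposures when it argues that the study is adequate, but promises no comparison between them. This stands too: the commitment is a descriptive breakdown.
- **First-exposure data exist elsewhere.** The active C-15 column helps, but only in the exposure-adjusted table and from another study. Listings and permitted exploratory analyses keep the split recoverable, though not pre-specified.
- **The groups are small.** True, but SAP 8.1 plans no formal testing, so low power is no reason to leave out a descriptive column.

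A reader might infer that the SAP drops the whole prior-treatment breakdown from every safety table. The documents do not support that. The tetrabenazine group remains. TMC and total motor score, which were safety parameters in the protocol, do get the split from Week 8. For C-SSRS, SAP 9.9.7 reports by treatment group, a term it does not define, so that table cannot be called unsplit with certainty.

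**Conclusion.** The mismatch holds on the text alone. Apart from the undefined C-SSRS grouping, SAP 9.9 specifies no prior SD-809 versus prior placebo split within Rollover, although Protocol 8.3 names these groups, and 8.10 does not declare the departure. It should be fixed, because it removes a planned view of titration safety that needs no new data.

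A reader might also infer that the pooled titration rate is biased. It is not shown to be. It estimates the endpoint as the protocol states it, and it differs from the first-exposure rate only if the two groups' rates differ, which the documents do not tell us. The gap of +31% to −16% rests wholly on assumed shares and risk ratios and includes zero. The gain from the fix is conformity with the protocol and transparency.

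Appendix 1 of the SAP is not shown, so this concerns the final-analysis tables only.

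**What to change.** In SAP 9.9.1, add prior-placebo and prior-SD-809 columns beside the retained Rollover total, using the groups already used in 9.7. At a minimum, do this for the TEAE overview, titration-period TEAEs by system organ class and preferred term, and the C-16 exposure-adjusted rates. For any safety table left without the split, declare and justify the departure in 8.10.

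Two wording points belong with this:

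- SAP 6 says "Unless specified otherwise, all data will be summarized for the Safety Population" and 9.9 says "Safety will be assessed using the Safety Population", while 8.7 calls for separate cohorts. State that an all-subjects column is produced, as the protocol requires.
- Define the C-SSRS groups in 9.9.7 as the same columns.

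The cost is SAP text and extra table columns. The downside is precision: the split columns are descriptive and would often not settle whether rates differ. Keeping the Rollover total beside them preserves the pooled precision.
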